6.2. Determination of Sample Size

Two groups of medications (Thrombin inhibitor, Factor Xa inhibitors) will be tested with the IVD and test results compared to LC-MS/MS results in urine.

The objective of the investigation is to show that the proportion of false negative and false positive tests with the IVD is below 5%.

Confidentiality Statement

This document is confidential and proprietary to Sponsor and HLZ Medizinische Statistik and for restricted circulation and access only. No part of it may be transmitted, reproduced, published or used by any person/s without prior written authorization.

To improve the strength of the study result, the following adjustments were made in the version 3.0 of the SAP compared to the version 2.0: $\alpha=0.01$ and a 2-sided test with a null proportion of 0.01.

The re-calculation of the required sample size remained unchanged compared to version 2.0 of the document to show that the assumed rate of 2.5% false-negative/false-positive tests is statistically significantly lower than 5% would require 440 patients per each test group including an assumed drop-out rate of 12%, with $\alpha=0.01$ and $\beta=0.20$ (80% power).

This sample size has been assessed with the SAS procedure PROC POWER (SAS Institute Inc., Cary, NC, USA, release 9.3) using the ONESAMPLEFREQ statement under the assumption that the test will be conducted as a 2-sided test with a null proportion of 0.01.

Remark to the calculation of the anticipated dropout rate: **As the present post marketing study is a non-invasive investigation, the dropout rate may be lower than expected.** Only patients fulfilling all of the inclusion criteria and none of the exclusion criteria will be included. Patient's written informed consent is part of the inclusion criteria.

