6.2.1 Primary Objective

- Assess the diagnostic performance of the IVD DOAC Dipstick test for oral direct Factor Xa and Thrombin inhibitors from urine samples of patients in comparison to the results of the concentration of the DOACs determined by liquid chromatography mass spectrometry (LC-MS/MS)

Confidentiality Statement

This document is confidential and proprietary to Sponsor and HLZ Medizinische Statistik and for restricted circulation and access only. No part of it may be transmitted, reproduced, published or used by any person/s without prior written authorization.

The flow chart for adjudication of eligible patients to group A (factor Xa inhibitors) and thrombin inhibitors is shown in the following figure:

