7.1 Inclusion Criteria

Remark: The first inclusion criterion of the Study Plan Version 7.0 eliminated and included into the exclusion criteria due to an overlap of the content.

- Fully signed and dated written informed consent
- Age >18 years
- Patient is either under therapy with Rivaroxaban, Apixaban, and Edoxaban or Dabigatran for at least 1 week

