10.1.11 Dropouts and Missing Data

Subject inclusion/exclusion criteria will be determined at baseline visit, and subjects who do not meet all criteria will not be entered into the study. Those subjects with signed informed consent deemed eligible to participate will be allocated a 2-digit number of the center at which patients are recruited followed by a 3-digit number that is consecutive according to the inclusion.

If patients do not fulfil posthoc all inclusion or exclusion criteria – except missing or late signature of written informed consent – e.g. reduced renal function, less than 7 days on therapy, intake of two different DOACs at the same time, change of dose of DOAC within the past 7 days and other findings, they will be evaluated individually and may be described as case reports.

If there is no "informed consent" or if the date of the "informed consent" is after the "start date" it is a dropout.

If a subject withdraws consent at any time after entering the study, will result in patient removal of all data from the study.

If data (dd.mm.yyyy) is specified with 99.99.yyyy in the table, it will be replaced as follows:

1. 99.99.yyyy (day and month missing) is replaced by 01.07.yyyy. Example: 99.99.2017 = 01.07.2017
2. 99.mm.yyyy (day missing) is replaced by 15.mm.yyyy. Example: 99.08.2018 = 15.08.2018

For twice daily intake of medication: If time (hour/min) is not specified, the mean of the time (i.e. 02:00 p.m. or 02:00 a.m., between 08:00 a.m. and 08:00 p.m. or 08:00 a.m. and 08:00 p.m.,

Confidentiality Statement

This document is confidential and proprietary to Sponsor and HLZ Medizinische Statistik and for restricted circulation and access only. No part of it may be transmitted, reproduced, published or used by any person/s without prior written authorization.

whatever applies according the documentation in the CRF, i.e. is taken for the analysis, respectively.

For once daily intake of medication: If time (hour/min) is not specified, the mean of the time (i.e. 08:00 p.m.) between 08:00 a.m. at the day before and the day of urine sampling is taken for analysis.

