10.2.2 Secondary Efficacy Variables

DOACs

- I. Comparison of the **qualitative DOAC Dipstick** results with the **qualitative** results of the **DOASENSE Reader** for DOACs

Statistical methods: determination of a cut-off value with Logistic regression analysis, McNemar test, kappa index, accuracy, sensitivity, specificity, positive and negative predictive values (with confidence intervals).

- II. Comparison of the **qualitative** results of the **DOAC Dipstick** with the **quantitative** results of **DOASENSE Reader**.

Statistical methods: determination of a cut-off value with Logistic regression analysis,

Confidentiality Statement

This document is confidential and proprietary to Sponsor and HLZ Medizinische Statistik and for restricted circulation and access only. No part of it may be transmitted, reproduced, published or used by any person/s without prior written authorization.

McNemar test, kappa index, accuracy, sensitivity, specificity, positive and negative predictive values (with confidence intervals).

III. Comparison of the **qualitative** results of the **DOASENSE Reader** with the **quantitative** results of **DOASENSE Reader**. Differences between readers have to be respected and if so, included into this analysis. Each center has an individual reader. Readers are standardized before delivery from the producer by adequate tastings, which, however do not include samples of patients under treatment. This has to be analyzed statistically in an adequate way. Number of samples may not be sufficient for all readers.

Statistical methods: determination of a cut-off value with Logistic regression analysis, McNemar test, kappa index, accuracy, sensitivity, specificity, positive and negative predictive values (with confidence intervals).

IV. Determination of the (kappa index, accuracy, sensitivity, specificity, positive and negative predictive values, cut-off value) **qualitative** results of the **DOAC Dipstick** compared to the **quantitative** results of **LC-MS/MS**.

- a. The results of rivaroxaban, apixaban and edoxaban have to be analysed separately because of different concentration ranges during therapy by LC-MS/MS. The results of the pad for factor Xa inhibitor of group B will be used to determine the statistical values. The results of the factor Xa inhibitors of group B by LC-MS/MS in urine will also be used for the statistical values.

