- b. The results of dabigatran are analysed from group B as well as from group A to determine the statistical values.

Statistical methods: determination of a cut-off value with Logistic regression analysis, McNemar test, kappa index, accuracy, sensitivity, specificity, positive and negative predictive values.

V. Comparison of the **qualitative** results of the **DOASENSE Reader** with the **quantitative** results of **LC-MS/MS**. The results of Rivaroxaban, Apixaban and Edoxaban have to be analyzed separately because of different concentration ranges

Confidentiality Statement

This document is confidential and proprietary to Sponsor and HLZ Medizinische Statistik and for restricted circulation and access only. No part of it may be transmitted, reproduced, published or used by any person/s without prior written authorization.

during therapy by LC-MS/MS.

Statistical methods: determination of a cut-off value with Logistic regression analysis, McNemar test, kappa index, accuracy, sensitivity, specificity, positive and negative predictive values.

VI. Comparison of the **quantitative** results of the **DOASENSE Reader** with the **quantitative** results of **LC-MS/MS** is performed. The results of Rivaroxaban, Apixaban and Edoxaban have to be analyzed separately because of different concentration ranges during therapy by LC-MS/MS.

Statistical method: t-test.

VII. Analysis of an **interaction of demographic data** on the results of **DOAC Dipstick**, **DOASENSE Reader** and **LC-MS/MS** (demographic data, creatinine)

Statistical method: multivariable regression analysis using SELECTION=FORWARD method

VIII. Analysis **dose, last intake and duration of treatment** with each DOAC on **qualitative** results of **DOAC Dipstick** and **DOASENSE Reader** and **quantitative** results of **LC-MS/MS**

Statistical method: multivariable regression analysis using SELECTION=FORWARD method

IX. Analysis of an **interaction of demographic data** on the results of **DOAC Dipstick**, **DOASENSE Reader** and **LC-MS/MS** (demographic data, creatinine)

Statistical method: multivariable regression analysis using SELECTION=FORWARD method

X. Analysis **dose, last intake and duration of treatment** with each DOAC on **qualitative** results of **DOAC Dipstick** and **DOASENSE Reader** and **quantitative** results of **LC-MS/MS**

Statistical method: multivariable regression analysis using SELECTION=FORWARD method

Confidentiality Statement

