18. LIST OF POST-TEXT-TABLES

Per protocol analysis

Tables

1. Demographic data of patients of group A and Group B, p values
2. Descriptive data of tested parameters per group
3. Results of regression analysis for Rivaroxaban with LC-MC/MC
4. Results of Regression analysis for Dabigatran with LC-MC/MC
5. Results of Regression analysis for Creatinine Jaffe Method
6. Results of Regression analysis of Urine Colour (REM% values)
7. Group A: correct and false negative and positive data of DOAC Dipstick versus LC-MS/MS, p-value
8. Group B: correct and false negative and positive data of DOAC Dipstick versus LC-MS/MS, p-values
9. Apixaban: correct and false negative and positive data of DOAC Dipstick versus LC-MS/MS, p-value
10. Edoxaban: correct and false negative and positive data of DOAC Dipstick versus LC-MS/MS, p-value
11. Rivaroxaban: correct and false negative and positive data of DOAC Dipstick versus LC-MS/MS, p-values
12. Group A: Creatinine: correct and false of low and normal data of DOAC Dipstick versus Jaffe-Method, p-value
13. Group B: Creatinine: correct and false of low and normal data of DOAC Dipstick versus Jaffe-Method, p-value
14. All analyses of no 3 to 13 with qualitative results DOAC Dipstick versus quantitative Results of DOAC Dipstick
15. Comparison of negative and positive or low and normal results of all pads of DOAC

Confidentiality Statement

This document is confidential and proprietary to Sponsor and HLZ Medizinische Statistik and for restricted circulation and access only. No part of it may be transmitted, reproduced, published or used by any person/s without prior written authorization.

Dipstick versus DOASENSE Reader

16. Comparison of quantitative values of all pads by DOASENSE Reader versus LC-MS/MS and Jaffe Method
17. Interaction of Apixaban, Edoxaban and Rivaroxaban results of DOAC Dipstick with results of Creatinine of DOAC Dipstick
18. Interaction of Apixaban, Edoxaban and Rivaroxaban and creatinine results of DOAC Dipstick with results of urine colour of DOAC Dipstick
19. Regression analysis of biographic data with pads of DOAC Dipstick to test interactions
20. Results of dependence of time of last intake of or drug on DOAC Dipstick quantitative, DOASENSE Reader qualitative and quantitative, and LC-MS/MS
21. Results of dose dependence of individual DOACs on parameters of No 20
22. Descriptive results of DOASENSE Control Urines and analysis of differences between centres

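### Item IV a of SAP section 10.2.2 names only group B for the per-drug factor Xa inhibitor analyses and omits group A, the patients who take these drugs

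*SAP*

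**What the plan says.** - Section 6.2, Determination of Sample Size, sets up two groups: "Two groups of medications (Thrombin inhibitor, Factor Xa inhibitors) will be tested with the IVD and test results compared to LC-MS/MS results in urine". The planned size is 440 per group, including an assumed 12% drop-out.
- Section 6.2.1 introduces the allocation figure with the words "group A (factor Xa inhibitors) and thrombin inhibitors". The figure is not available here, and the sentence does not use the label group B.
- Section 7.1 states eligibility as "Patient is either under therapy with Rivaroxaban, Apixaban, and Edoxaban or Dabigatran for at least 1 week". Section 10.1.11 lists "intake of two different DOACs at the same time" among the findings that lead to individual evaluation and possibly a case report.
- Section 10.2.2, item IV, compares the visual dipstick with LC-MS/MS. It asks for kappa, accuracy, sensitivity, specificity, both predictive values and a cut-off value.
- Item IV a requires the three factor Xa inhibitors to be analysed separately and then says: "The results of the pad for factor Xa inhibitor of group B will be used to determine the statistical values". The following sentence gives group B as the source of the factor Xa inhibitor LC-MS/MS values too. Group A does not appear in IV a.
- Item IV b, for the thrombin inhibitor, says: "The results of dabigatran are analysed from group B as well as from group A to determine the statistical values".
- Row 5a of the output table in section 10.1.5 and tables 9 to 11 in section 18 plan dipstick accuracy against LC-MS/MS for apixaban, edoxaban and rivaroxaban.

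**The concern.** An accuracy analysis needs samples that the reference method calls positive and samples that it calls negative. For a factor Xa inhibitor the positives come almost entirely from patients who take that drug, and those patients are in group A. Item IV a assigns both the index result (the factor Xa pad) and the reference result (LC-MS/MS) to the other group. A programmer who follows the text would build three per-drug tables with an empty reference-positive margin.

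At stake are the per-drug sensitivity and the per-drug cut-off. These are the reason that IV a gives for separating the drugs, since it points to their different concentration ranges under treatment. Section 11 also says that the SAP prevails where it and the protocol disagree, so a clearer protocol sentence would not settle the matter.

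**Working it through.** The plan gives no figure for this point, so there is none to reproduce. The check traces the groups and counts the reference positives that IV a would supply.

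**Step 1: who is in group B.** There are two medication groups (section 6.2) and group A is the factor Xa inhibitor group (section 6.2.1). By elimination group B is the thrombin inhibitor group, dabigatran. Item IV b fits this.

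**Step 2: size of group B.** 440 × (1 − 0.12) = 387.2, about 387 evaluable. The 440 is taken as stated and serves only as illustration.

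**Step 3: reference positives in group B.** LC-MS/MS is positive above 4.0 ng/ml, optionally 8 ng/ml (section 8.4). Patients take a factor Xa inhibitor or dabigatran (section 7.1), and those found on two DOACs are handled individually (section 10.1.11). The expected number of factor Xa inhibitor positives in group B is therefore about 0 of 387.

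**Step 4: what item IV yields from group B alone**, with TP = FN = 0.
- Sensitivity = TP/(TP + FN) = 0/0, undefined for each drug.
- Cut-off: no samples lie above the normal range, so none can be fitted.
- PPV = TP/(TP + FP) = 0/FP, which is 0 if the pad gives any false positive.
- Kappa: observed agreement is TN/n. Expected agreement is (TN/n) × 1 + (FP/n) × 0 = TN/n. Kappa is therefore 0 whenever FP > 0.
- Specificity = TN/(TN + FP) can be estimated.

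Section 8.2 also calls a strip invalid when pads 3 and 4 are both positive, so a valid pad 3 positive in a dabigatran patient is rarer still.

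**Step 5: sensitivity to unexpected positives (assumed rates).** If every positive is detected, the exact two-sided 95% lower limit for k of k is 0.025^(1/k).

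| Assumed share of group B positive | Positives, all three drugs together | Lower 95% limit if all detected |
|---|---|---|
| 0% | 0 | undefined |
| 0.5% | 2 | 15.8% |
| 1% | 4 | 39.8% |
| 2% | 8 | 63.1% |

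**Step 6: with group A included.** The SAP gives no per-drug numbers, so these are assumptions, with about 97.5% detected and exact (Clopper-Pearson) 95% intervals.
- 50 positives, 49 detected: 89.4% to 99.9%.
- 129 positives, 126 detected: 93.4% to 99.5%.
- 200 positives, 195 detected: 94.3% to 99.2%.
- Specificity, for example 377 of 387 group B negatives: 95.3% to 98.8%.

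**The case against.** The strongest reply is that IV a does not say group B alone. It omits group A without excluding it. Its opening sentence presupposes patients under treatment with the three drugs. Item IV b, row 5a and tables 9 to 11 all point to both groups being used, with group B as the drug-free comparison. A sensible analyst would probably read it that way. This stands as an account of what was meant, and it makes a drafting omission the likeliest cause. It does not rescue the wording: IV a names a source for the pad result and for the reference result, and both times it is group B.

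The identity of group B is also inferred, because the allocation figure is not available. The inference from sections 6.2, 6.2.1 and 10.2.2 is strong.

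A reader might go further in two ways that the SAP does not support.
- One might infer that the split by group in tables 7 and 8 ("Group A: correct and false negative and positive data of DOAC Dipstick versus LC-MS/MS, p-value") leaves the factor Xa pad almost without drug-negative samples, so that its false-positive rate is lost. Those titles name no pad, and section 10.1.5 has all four pads evaluated in every patient. Rows 3, 4 and 5a of the same section plan accuracy by drug class and by drug with no group restriction.
- One might call PPV and kappa undefined alongside sensitivity. Step 4 shows that with any false positive on the pad both equal 0, which is uninformative but defined.

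**Conclusion.** Wrong as written, in a secondary analysis. Taken literally, item IV a has about 0 reference positives among about 387 evaluable samples. Per-drug sensitivity is 0/0, no cut-off can be fitted, PPV and kappa say nothing, and only specificity can be estimated. The item also contradicts item IV b, row 5a and tables 9 to 11.

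The conclusion rests on group B being the dabigatran patients and on very few of them having a factor Xa inhibitor in urine. At an assumed 2% there would be only 8 positives over the three drugs.

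It would be a mistake to conclude that the trial cannot estimate sensitivity for factor Xa inhibitors. The group A data will be collected, and the primary analysis in section 10.2.1 covers both drug classes, with its own cut-off step and no group restriction. This defect does not touch it.

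**What to change.** Reword item IV a to parallel IV b. For each factor Xa inhibitor, analyse the pad 3 and LC-MS/MS results of the group A patients on that drug together with those of group B. State that every sample is classified as positive or negative by its LC-MS/MS result, not by the prescribed drug. This matters because section 10.1.5 makes LC-MS/MS the gold standard, and row 11 of its output table anticipates treated patients who are negative on both LC-MS/MS and the dipstick. A rule that takes positives from group A and negatives from group B could be read as fixing reference status by prescription, which would misclassify such patients. State also that tables 9 to 11 use this combined set, and define group B in words where group A is first named.

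The cost is a few sentences of SAP text and notes to three tables. No new data or samples are needed.

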8.3 Assessment of DOAC Dipstick by DOASENSE Reader

Measurement

After the urine strip has been immersed in the urine sample for approx. 2-3 seconds according to the instructions for use, the strip is placed on the strip holder of the DOASENSE Reader after 10 minutes and the START button is pressed. The device pulls the strip holder and carries out the measurement. The result of the four pads is displayed on the screen and printed on the thermal printer. After measuring the strip, the device ejects the strip holder. The strip is removed and disposed of.

The output of DOASENSE Reader are 3-digit values reprinting the %REM values (reflectance units) of the 4 pads and printed by the Reader of the printer for each measurement that is attached with an adhesive by the study personal into the CRF. These values are then written with a ball point pen on the right part of the printed values because the printout may lose color over time.

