8.4 Analysis by LC-MS/MS

Urine samples will be analyzed at Laboratory Limbach by LC-MS/MS. The method is described elsewhere (23). The results are given as ng/ml. Normal range of values is 0.1 to 4.0 ng/ml (23). Normal values are interpreted as “negative”. Higher values represent “positive” results. Optionally, the upper limit of normal range may be changed to 8 ng/ml if values between 4 ng/ml and 8 ng/ml occur in more than 0.5% of patients.

Methodological reasons may lead to a repeated measurement of the urine sample diluted 1:15. Analyses will be repeated with this dilution if concentration of DOAC in urine is > 50.000 ng/ml or is expected to be above this value. The repetition is required to ensure that the concentration is in the linear range of detection range of LC-MS/MS. However, the dilution affects the normal range, which is 15-fold higher compared to samples that are

Confidentiality Statement

This document is confidential and proprietary to Sponsor and HLZ Medizinische Statistik and for restricted circulation and access only. No part of it may be transmitted, reproduced, published or used by any person/s without prior written authorization.

analysed without this dilution. For the statistical evaluation these mean of the normal range without dilution will be used.

Remark: The personal at Limbach laboratory is blinded regarding the information which DOAC the patient is taken. The personal does not have access to any information in the CRF which DAOC the patient was taking.

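### A t-test of Reader reflectance against LC-MS/MS concentration cannot show whether the Reader tracks concentration; McNemar between the two drug groups also lacks pairs

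*SAP*

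**What the plan says.** **Reader against LC-MS/MS.** SAP section 10.2.2, item VI, sets the quantitative Reader result against the quantitative LC-MS/MS result and adds: "The results of Rivaroxaban, Apixaban and Edoxaban have to be analyzed separately because of different concentration ranges during therapy by LC-MS/MS". The only method named is "Statistical method: t-test".

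Section 8.3 describes the Reader output as "3-digit values reprinting the %REM values (reflectance units) of the 4 pads". For LC-MS/MS, section 8.4 states "The results are given as ng/ml". It sets the upper limit of a negative result at 4.0 ng/ml and plans a diluted repeat "if concentration of DOAC in urine is > 50.000 ng/ml".

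In section 18, Table 16 is "Comparison of quantitative values of all pads by DOASENSE Reader versus LC-MS/MS and Jaffe Method", with no method. Tables 3 and 4 are "Results of regression analysis for Rivaroxaban with LC-MC/MC" and "Results of Regression analysis for Dabigatran with LC-MC/MC". Neither names the Reader, and there is no such table for apixaban or edoxaban.

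**Between medications.** The general methods in section 10.1.5 plan McNemar tests to compare sensitivity, specificity and accuracy between the two medications, and chi-square or Fisher's exact tests for the predictive values. Under section 7.1 a patient takes either a factor Xa inhibitor or dabigatran. All tests are two-sided at 0.01.

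**The concern.** Item VI concerns two continuous measurements on the same urine. The useful question is whether reflectance moves with concentration, and how closely. On its plain reading a t-test asks whether the mean reflectance equals the mean concentration. That has no meaning across units, and the answer changes if ng/ml becomes µg/ml. A p-value below 0.01 could be read as a finding about the Reader when it reflects only the scales. Item VI is the only numbered analysis of the quantitative Reader value against the reference method; item V uses the qualitative Reader result.

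McNemar's test needs two results on each patient. Sensitivity for factor Xa inhibitors comes from patients taking one of them, and sensitivity for dabigatran from patients taking dabigatran. Those sets are disjoint, and the LC-MS/MS-negative sets are essentially disjoint too. Any paired table would rest on an arbitrary matching of unrelated patients.

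**Working it through.** The SAP gives no figure for item VI to reproduce, so the check shows how the named test behaves.

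**Inputs.** From the SAP: 440 per group with 12% drop-out, so 440 × 0.88 = 387; two-sided 0.01; the units and limits in sections 8.3 and 8.4. Assumed, because the SAP does not give them: three equal factor Xa groups (387 / 3 = 129); log-normal concentration; %REM = 50 − 6z + noise with SD 2. Here z is the standardised log concentration when the Reader tracks, or an independent draw when it does not.

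**One case by formula** (median 1000 ng/ml, log-SD 1).
- Concentration: mean = 1000 × e^0.5 = 1648.7; SD = 1648.7 × √(e − 1) = 2161.2.
- Reader: mean 50, variance 36 + 4 = 40.
- Two-sample t in ng/ml: (50 − 1648.7) / √((40 + 2161.2²)/129) = −1598.7 / 190.3 = −8.4.
- Same data in µg/ml: (50 − 1.65) / √((40 + 2.1612²)/129) = 48.35 / 0.588 = +82.

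No covariance enters the two-sample statistic, so tracking cannot affect its expected size. The unit changes even its sign.

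**Simulation of the two-sample test, n = 129, log-SD 1.** Share of runs with p < 0.01:

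| Median (ng/ml) | Tracks | Unrelated | Median t, ng/ml | Median t, µg/ml |
|---|---|---|---|---|
| 50 | 91% | 92% | −3.6 | +90 |
| 100 | 99.9% | 100% | −6.6 | +90 |
| 1000 | 100% | 100% | −9.3 | +83 |
| 10,000 | 100% | 100% | −9.6 | +19 |

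The simulated −9.3 exceeds the formula's −8.4 in size because a skewed sample's SD usually falls below the population SD. Spearman's correlation (median −0.94 when tracking) gives p < 0.01 in 100% of tracking runs and 0.9% of unrelated runs.

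**Wider range.** If 4 and 50,000 ng/ml are taken as the 2.5th and 97.5th percentiles, the median is √(4 × 50,000) = 447 and the log-SD is ln(50,000/4)/3.92 = 2.41. The t-test rejects in 63% of runs in both cases (95% in both in µg/ml). Spearman rejects in 100% against 1.1%.

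**Paired t-test.** Its variance contains −2 × covariance. In the case above the covariance is −6 × 1648.7 = −9892, so the added term is 19,784 against 4,670,825, or 0.4%. In simulation the paired test rejects in 89% (tracks) and 93% (unrelated) at median 50 ng/ml, and in 63% of both in the wider range.

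**Feasibility of the replacement.** By Fisher's z, r = 0.9 has a 95% interval of 0.86 to 0.93 at n = 129 (standard error 1/√126) and 0.80 to 0.95 at n = 30 (1/√27).

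**McNemar.** As an illustration, take the SAP's 2.5% and 5% as false-negative rates with all 387 per group LC-MS/MS-positive: 0.025 × 387 ≈ 10 and 0.05 × 387 ≈ 19. Under random matching, the number of false negatives that fall together is hypergeometric:

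| Paired | Probability | Discordant | Exact McNemar p |
|---|---|---|---|
| 0 | 0.601 | 19 v 10 | 0.136 |
| 1 | 0.318 | 18 v 9 | 0.122 |
| 2 | 0.072 | 17 v 8 | 0.108 |

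These cover 99.0% of matchings, and the mean p over all matchings is 0.129. Fisher's exact test gives 0.129 and chi-square without correction 0.088. A McNemar p below 0.01 needs all 10 paired, which has probability 5 × 10⁻¹⁵.

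**The case against.** **Item VI supports no stated objective directly.** The Reader objectives in section 6.2.2 are agreement with the visual reading, and sensitivity and specificity against LC-MS/MS. Items I and V serve these with suitable methods. This is true and limits the consequence. Item VI is still a listed secondary analysis with a method that cannot answer it.

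**The pairing is ignored.** A paired t-test does contain the covariance, so it is not strictly blind to association. At a median of 1000 ng/ml expressed in µg/ml, its median t is 69 when tracking and 83 when not. The exact equality therefore applies only to the two-sample test. The paired test still rejects about equally often in both cases.

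**Tables 3 and 4 may belong elsewhere.** They do not name the Reader and could report the cut-off regressions. That is fair. It also means that they cannot be relied on to supply what item VI lacks.

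**The scales are assumed.** They are, and the percentages move with them. The dependence on units does not.

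**Section 10.1.5 lets unsuitable methods be replaced, with the change documented in the study report.** Disclosure helps, but the clause names no substitute and leaves the choice until the data are in hand. The mismatch is visible now.

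**Part of the McNemar plan is sound.** All pads are read in every urine, so the overall accuracy of pad 3 against pad 4 can be paired. The text may also have meant methods within each medication. Both points stand, and the criticism is confined to sensitivity and specificity between medications.

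**Conclusion.** The concern holds and should be fixed. As written, item VI cannot show whether the Reader tracks concentration: rejection rates are nearly the same with and without tracking (91% v 92% and 63% v 63% in the settings where they are not close to 100%), while a rank correlation separates the two cases almost completely. The percentages rest on the assumed sample split, reflectance model and concentration distributions. The conclusion rests only on the two units. If a t-test of a slope or correlation was meant, the SAP does not say so.

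The McNemar plan for sensitivity and specificity between medications is invalid because the patients differ, but its practical effect is small. The primary analysis, item V and the sample size are untouched by either point.

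**What to change.** - **Item VI:** replace the t-test with Spearman's correlation, a regression of %REM on log concentration, or both, for each DOAC including apixaban and edoxaban. Allow for Reader or centre, and state how values at or below the detection limit are handled.
- **Section 18:** have Table 16 name this method, and either extend the regression tables to all four DOACs or state that Tables 3 and 4 serve another analysis.
- **Section 10.1.5:** compare sensitivity and specificity between medications by chi-square or Fisher's exact test, both already named there, or by a difference in proportions with a confidence interval. Keep McNemar for comparisons on the same urine, including overall accuracy of pad 3 against pad 4. If a comparison of methods within each medication was intended, say so.

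Both changes belong in the SAP before database lock. They cost wording and minor programming, need no new data, and leave the primary analysis and sample size as they are.
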